14.2.27 Sensitivity analysis

This section outlines the possible event and censoring dates for progression, as well as addresses the issues of missing tumor assessments during the study. For instance, if one or more assessment visits are missed prior to the progression event, to what date should the progression event be assigned? And should progression event be ignored if it occurred after a long period of a patient being lost to follow-up? It is important that the protocol and SAP specify the primary analysis in detail with respect to the definition of event and censoring dates and also include a description of one or more sensitivity analyses to be performed.

Based on definitions outlined in [Section 14.2.25](#), and using the draft FDA guideline on endpoints ([Clinical Trial Endpoints for the Approval of Cancer Drugs and Biologics-April 2005](#)) as a reference, the following analyses can be considered:

[figure not shown]

Table 14-7 Options for event dates used in PFS, TTP, duration of response

Situation		Options for end-date (progression or censoring) ¹ (1) = default unless specified differently in the protocol or SAP	Outcome
A	No baseline assessment	(1) Date of randomization/start of treatment ³	Censored
B	Progression at or before next scheduled assessment	(1) Date of progression (2) Date of next scheduled assessment ²	Progressed Progressed
C1	Progression or death after exactly one missing assessment	(1) Date of progression (or death) (2) Date of next scheduled assessment ²	Progressed Progressed
C2	Progression or death after two or more missing assessments	(1) Date of last adequate assessment ² (2) Date of next scheduled assessment ² (3) Date of progression (or death)	Censored Progressed Progressed
D	No progression	(1) Date of last adequate assessment	Censored
E	Treatment discontinuation due to 'Disease progression' without documented progression, i.e. clinical progression based on investigator claim	(1) N/A (2) Date of discontinuation (visit date at which clinical progression was determined)	Ignored Progressed
F	New anticancer therapy given	(1) Date of last adequate assessment (2) Date of secondary anti-cancer therapy (3) Date of secondary anti-cancer therapy (4) N/A	Censored Censored Event Ignored
G	Deaths due to reason other than deterioration of 'Study indication'	(1) Date of last adequate assessment	Censored (only TTP and duration of response)

¹. =Definitions can be found in Section 14.2.25.
 
². =After the last adequate tumor assessment. "Date of next scheduled assessment" is defined in Section 14.2.25.
 
³. =The rare exception to this is if the patient dies no later than the time of the second scheduled assessment as defined in the protocol in which case this is a PFS event at the date of death.
			

[figure not shown]
The primary analysis and the sensitivity analyses must be specified in the protocol. Clearly define if and why options (1) are not used for situations C, E and (if applicable) F.

Situations C (C1 and C2): Progression or death after one or more missing assessments: The primary analysis is usually using options (1) for situations C1 and C2, i.e.

- (C1) taking the actual progression or death date, in the case of only one missing assessment.
- (C2) censoring at the date of the last adequate assessment, in the case of two or more consecutive missing assessments.

In the case of two or missing assessments (situation C2), option (3) may be considered jointly with option (1) in situation C1 as sensitivity analysis. A variant of this sensitivity analysis consists of backdating the date of event to the next scheduled assessment as proposed with option (2) in situations C1 and C2.

Situation E: Treatment discontinuation due to 'Disease progression' without documented progression: By default, option (1) is used for situation E as patients without documented PD should be followed for progression after discontinuation of treatment. However, option (2) may be used as sensitivity analysis. If progression is claimed based on clinical deterioration instead

of tumor assessment by e.g. CT-scan, option (2) may be used for indications with high early progression rate or difficulties to assess the tumor due to clinical deterioration.

Situation F: New cancer therapy given: the handling of this situation must be specified in detail in the protocol. However, option (1), i.e. censoring at last adequate assessment may be used as a default in this case.

Additional suggestions for sensitivity analyses

Other suggestions for additional sensitivity analyses may include analyses to check for potential bias in follow-up schedules for tumor assessments, e.g. by assigning the dates for censoring and events only at scheduled visit dates. The latter could be handled by replacing in [Table 14-7](#) the “Date of last adequate assessment” by the “Date of previous scheduled assessment (from baseline)”, with the following definition:

- **Date of previous scheduled assessment (from baseline)** is the date when a tumor assessment would have taken place, if the protocol assessment scheme was strictly followed from baseline, immediately before or on the date of the last adequate tumor assessment.

In addition, analyses could be repeated using the Investigators’ assessments of response rather than the calculated response. The need for these types of sensitivity analyses will depend on the individual requirements for the specific study and disease area and have to be specified in the protocol or SAP documentation.

14.2.28 Data handling and programming rules

The following section should be used as guidance for development of the protocol, data handling procedures or programming requirements (e.g. on incomplete dates).

14.2.29 Study/project specific decisions

[figure not shown]
For each study (or project) various issues need to be addressed and specified in the protocol or SAP documentation. Any deviations from protocol must be discussed and defined at the latest in the SAP documentation.

The proposed primary analysis and potential sensitivity analyses should be discussed and agreed with the health authorities and documented in the protocol (or at the latest in the SAP documentation before database lock).

14.2.30 End of treatment phase completion

Patients **may** voluntarily withdraw from the study treatment or may be taken off the study treatment at the discretion of the investigator at any time. For patients who are lost to follow-up, the investigator or designee should show "due diligence" by documenting in the source documents steps taken to contact the patient, e.g., dates of telephone calls, registered letters, etc.

The end of treatment visit and its associated assessments should occur within 14 days of the last study treatment.

Patients may discontinue study treatment for any of the following reasons:

- Adverse event(s)
- Lost to follow-up
- Physician decision
- Pregnancy
- Protocol deviation
- Technical problems
- Subject/guardian decision
- Death
- Progressive disease
- Study terminated by Novartis
- Non-compliant with study treatment
- No longer requires treatment
- Treatment duration completed as per protocol (optional, to be used if only a fixed number of cycles is given)

14.2.31 End of post-treatment follow-up (study phase completion)

End of post-treatment follow-up visit will be completed after discontinuation of study treatment and post-treatment evaluations but prior to collecting survival follow-up.

Patients may provide study phase completion information for one of the following reasons:

- Adverse event
- Lost to follow-up
- Physician decision
- Pregnancy
- Protocol deviation
- Technical problems
- Subject/guardian decision
- Death
- New therapy for study indication
- Progressive disease
- Study terminated by Novartis

14.2.32 Medical validation of programmed overall lesion response

As RECIST is very strict regarding measurement methods (i.e. any assessment with more or less sensitive method than the one used to assess the lesion at baseline is considered UNK) and not available evaluations (i.e. if any target or non-target lesion was not evaluated the whole overall lesion response is UNK unless remaining lesions qualified for PD), these UNK assessments may be re-evaluated by clinicians at Novartis or external experts. In addition, data review reports will be available to identify assessments for which the investigators' or central

reader's opinion does not match the programmed calculated response based on RECIST criteria. This may be queried for clarification. However, the investigator or central reader's response assessment will never be overruled.

If Novartis elect to invalidate an overall lesion response as evaluated by the investigator or central reader upon internal or external review of the data, the calculated overall lesion response at that specific assessment is to be kept in a dataset. This must be clearly documented in the SAP documentation and agreed before database lock. This dataset should be created and stored as part of the 'raw' data.

Any discontinuation due to 'Disease progression' without documentation of progression by RECIST criteria should be carefully reviewed. Only patients with documented deterioration of symptoms indicative of progression of disease should have this reason for discontinuation of treatment or study evaluation.

14.2.33 Programming rules

The following should be used for programming of efficacy results:

14.2.34 Calculation of 'time to event' variables

Time to event = end date - start date + 1 (in days)

When no post-baseline tumor assessments are available, the date of randomization/start of treatment will be used as end date (duration = 1 day) when time is to be censored at last tumor assessment, i.e. time to event variables can never be negative.

14.2.35 Incomplete assessment dates

All investigation dates (e.g. X-ray, CT scan) must be completed with day, month and year.

If one or more investigation dates are incomplete but other investigation dates are available, this/these incomplete date(s) are not considered for calculation of the assessment date (and assessment date is calculated as outlined in [Section 14.2.25](#)). If all measurement dates have no day recorded, the 1st of the month is used.

If the month is not completed, for any of the investigations, the respective assessment will be considered to be at the date which is exactly between previous and following assessment. If a previous and following assessment is not available, this assessment will not be used for any calculation.

14.2.36 Incomplete dates for last known date patient alive or death

All dates must be completed with day, month and year. If the day is missing, the 15th of the month will be used for incomplete death dates or dates of last contact.

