- Date of last contact is defined as the last date the patient was known to be alive. This corresponds to the latest date for either the visit date, lab sample date or tumor assessment date. If available, the last known date patient alive from the survival follow-up page is used. If no survival follow-up is available, the date of discontinuation is used as last contact date.
- Date of secondary anti-cancer treatment is defined as the start date of any additional (secondary) antineoplastic therapy or surgery.

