2.6 Analysis supporting secondary objectives

2.6.1 Efficacy objectives

The secondary objective is to assess the efficacy of NIR178 in combination of PDR001 using ORR per iRECIST, and other efficacy measures including disease control rate (DCR), duration of response (DOR), progression free survival (PFS) and 2 year overall survival (OS) by both RECIST v1.1 and iRECIST for solid tumors, by PCWG3 guidance (see Protocol Appendix 5) for mCRPC, and by [Cheson et al \(2014\)](#) for DLBCL.

These efficacy endpoints will be summarized for all the treatment groups contributing to the analysis of primary efficacy objective (see [Section 2.1](#) general analysis conventions).

ORR:

Overall response rate (ORR) is defined as the proportion of patients with best overall response (BOR) of immuno-related complete response (iCR) or immuno-related partial response (iPR), as per local review and according to iRECIST (see Protocol Appendix 3 for details) for solid tumors.

ORR as per iRECIST will be provided for each treatment indication along with corresponding 95% confidence interval (CI).

DCR:

DCR is the proportion of patients with a best overall response of CR, PR or stable disease (SD). DCR will be summarized by treatment indication with accompanying 95% confidence intervals.

OS, PFS and DOR:

OS is defined as the time from date of start of treatment to date of death due to any cause. If a patient is not known to have died, OS time will be censored at the date of last contact. The 2 year OS rate is the proportion of patients with at least 2 years of OS.

PFS is defined as the time from start of treatment date to date of the first documented disease progression or date of death, whichever happens first. If a patient has not had the event at the date of analysis cut-off, PFS will be censored at the time of the adequate tumor assessment before the cut-off.

For patients with a confirmed CR or confirmed PR, the DoR is the time from date of first documented response (CR or PR) to date of first documented progression or death due to underlying cancer, whichever happens first. If progression or death has not occurred at the date of analysis cut-off, then DoR will be censored at the date of last adequate tumor assessment before the cut-off.

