5.1 Imputation rules

5.1.1 Study drug

The following rule applies to daily dosing and should be used for the imputation of the dose end date for a given study treatment component:

Scenario 1: If the dose end date is completely missing and there is no EOT page and no death date, the patient should be treated as on-going, and the cut-off date should be used as the dose end date. This scenario should not be applicable for final CSR. All patients should have EOT page complete before the Database lock for Final CSR.

Scenario 2: If the dose end date is completely or partially missing and the EOT page is available: Please note that date of assessment on EOT CRF might be very different from last date of dose.

Case 1: The dose end date is completely missing, and the EOT completion date is complete, then this latter date should be used.

Case 2: Only Year(yyyy) of the dose end date is available and yyyy < the year of EOT date:

Use Dec31yyyy

Case 3: Only Year(yyyy) of the dose end date is available and yyyy = the year of EOT date:

Use EOT date

Case 4: Both Year(yyyy) and Month (mm) are available for dose end date, and yyyy = the year of EOT date and mm < the month of EOT date:

Use last day of the Month (mm)

All other cases should be considered as a data issue and the statistician should contact the data manager of the study.

After imputation, compare the imputed date with start date of treatment, if the imputed date is < start date of treatment:

Use the treatment start date

Patients with missing start dates are to be considered missing for all study treatment component related calculations and no imputation will be made. If start date is missing, then end-date should not be imputed.

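### The 15th-of-month rule for partial death and last-contact dates has no floor at treatment start or at later evidence of life, so it can give zero or negative OS and shorten PFS

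*Protocol*

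**What the plan says.** Protocol Appendix 2, section 14.2.36, opens with a data standard, "All dates must be completed with day, month and year", and then gives the fallback: "If the day is missing, the 15th of the month will be used for incomplete death dates or dates of last contact". No exception or lower bound follows.

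Section 14.2.34 counts days inclusively, as end date minus start date plus 1. It notes that a patient censored at the start date has a duration of 1 day, and concludes that "time to event variables can never be negative".

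The imputed date feeds the secondary endpoints in SAP 2.6.1. For OS: "OS is defined as the time from date of start of treatment to date of death due to any cause". PFS ends at the "date of the first documented disease progression or date of death, whichever happens first". OS without a known death is censored at last contact, and Protocol 14.2.25 ranks the sources for that date: "If available, the last known date patient alive from the survival follow-up page is used".

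SAP 5.1 has imputation rules for dose-end, adverse-event, concomitant, prior and post-therapy, diagnosis and tumor-assessment dates. It has none for death or last contact, so nothing in the two documents overrides 14.2.36. Elsewhere the SAP does apply a floor. For the dose-end date, section 5.1.1 says "After imputation, compare the imputed date with start date of treatment, if the imputed date is < start date of treatment", and in that case the treatment start date is used. For adverse events that began after treatment start, or may have, section 5.1.2 does not let an imputed start in the month of first dose fall on or before the first dose.

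**The concern.** A mid-month default is a normal choice, but it is usually bounded by what is already known about the patient. Here the 15th applies even when the first dose, a visit, a laboratory sample or a scan is recorded later in the same month. The derived data can then contain a death before the first dose or before a scan of a living patient.

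OS, PFS and duration of response all depend on the date. Kaplan-Meier summaries are planned for treatment groups of 10 or more patients, and most Part 1 groups have at most 30, so a single impossible time would be noticeable. The last-contact half of the rule matters for the same reason: a partial date on the survival page replaces a later, complete scan date.

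**Working it through.** **Inputs.** The 15th rule (Protocol 14.2.36); T = end - start + 1 (14.2.34); the OS and PFS definitions (SAP 2.6.1); the order of sources for last contact (Protocol 14.2.25). Worked dates are in 2020; for the cases that span February, a non-leap year makes each figure one day smaller.

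**1. The plan's own figure.** With end = start, T = 0 + 1 = 1 day, as 14.2.34 states.

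**2. First dose and death in the same month.** Death is recorded as March and set to 15 March.

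| First dose | OS = 15 - day + 1 |
|---|---|
| 15 March | 1 |
| 16 March | 0 |
| 17 March | -1 |
| 20 March | -4 |
| 31 March | -15 |

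OS is 0 for a first dose on the 16th and negative from the 17th.

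**3. Size of the error.** A true death on the 31st is dated 31 - 15 = 16 days too early; one on the 1st is dated 15 - 1 = 14 days too late. If the day of death is uniform over a 30-day month, the average error is 15.5 - 15 = 0.5 day.

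**4. Effect on PFS.** Treatment starts 10 January, a scan on 20 March shows progression, and the patient dies on 28 March with only the month recorded.
- Documented PFS: 10 January to 20 March = 21 + 29 + 20 + 1 = 71 days.
- True OS: 21 + 29 + 28 + 1 = 79 days.
- Imputed OS: 21 + 29 + 15 + 1 = 66 days.
- PFS as derived: the earlier of 20 March and 15 March is 15 March, so 66 days.

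The imputed death displaces a documented progression, and PFS loses 5 days.

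**5. Last-contact route.** Same start, stable disease on a scan of 20 March, survival page recorded as March. Last contact becomes 15 March, because the survival page takes precedence. OS is censored at 66 days. PFS is censored at the last adequate scan, 71 days.

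**6. How often a death is dated before the last evidence of life.** The documents give no figure. Assume the day of death is uniform on 1 to 30 and the gap from last evidence of life to death is uniform on 0 to G days, with G at least 14. For death on day d = 16 to 30, d - 15 of the G + 1 gaps put the last evidence after the 15th. The sum 1 + 2 + ... + 15 is 120, so the share is 120 / [30(G + 1)].
- G = 14: 120/450 = 26.7%.
- G = 84 (12 weeks): 120/2,550 = 4.7%.

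Within the affected deaths the mean understatement is 1,240/120 = 10.3 days, where 1,240 is the sum of squares from 1 to 15.

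**7. With a floor at the latest known-alive date.** First dose 20 March, death March: OS = 1 day instead of -4. The case in step 4: OS = 71 and PFS = 71. The case in step 5: OS and PFS are both censored at 71.

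**The case against.** The case for leaving the rule alone is reasonable. Complete dates are required first, and Protocol 9.4 has missing values queried. Negative OS needs a first dose on the 17th or later and a death before the month ends, when visits are frequent and a missing day is least likely. Over all missing-day deaths the 15th is nearly unbiased (step 3). Protocol 14.2.28 calls the section guidance, and the programming dataset specifications named in the SAP introduction are not available here and may contain a check. The non-negativity statement in 14.2.34 is explained only for patients with no post-baseline tumor assessment.

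All of this limits the impact. It does not supply the missing floor: the rule as written still produces the results in steps 2, 4 and 5, and the SAP bounds comparable dates but not these.

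Four stronger readings are tempting, and the documents do not support them:
- **OS shorter than PFS after a partial death date.** PFS takes the earlier of progression and death, so it falls to the same imputed date and equals OS. The inversion arises only through last contact, or if a program ignores the PFS definition.
- **14.2.34 as a bar on OS below PFS.** It excludes negative times only.
- **Deaths moving between on-treatment and post-treatment tables.** SAP 2.1.1.5 assigns dates too incomplete to classify to the on-treatment period, so such movement is not established.
- **About a quarter of missing-day deaths being affected.** That needs a gap of no more than 14 days. With survival contact every 12 weeks (Protocol 7.1.7), the share is nearer 5%.

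**Conclusion.** The point holds as a defect in a date rule. Without a floor, 14.2.36 can yield OS of 0 to -15 days, can date a death before a scan of a living patient and so shorten PFS (and duration of response, where the death is from the underlying cancer), and can censor OS before PFS through a partial last-contact date.

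The practical weight is low. Depending on the assumed gap, roughly 5% to 27% of missing-day deaths would be dated before the last evidence of life; the number of missing-day deaths is unknown. The endpoints concerned are summarised descriptively, and no go/no-go rule uses them. The conclusion assumes that the unseen dataset specifications contain no overriding check.

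**What to change.** Add one rule to SAP 5.1: when the day of death or of last contact is missing, impute the latest of (a) the 15th of the recorded month, (b) the treatment start date and (c) the last complete date on which the patient is known alive from a visit, laboratory sample, scan or dose.

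Use the known-alive date itself, not the day after. Adding a day would turn a scan on 31 March with death in March into a death on 1 April, and would censor last contact beyond any evidence of life. If the floor for a death falls in a later month than the one recorded, the record is inconsistent and should be queried rather than imputed.

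The cost is one sentence and one line of code, through the SAP amendment (before database lock) or addendum (after it) that the SAP introduction already provides for. No data collection changes.

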14.2.37 Non-target lesion response

If no non-target lesions are identified at baseline (and therefore not followed throughout the study), the non-target lesion response at each assessment will be considered 'not applicable (NA)'.

14.2.38 Study/project specific programming

The standard analysis programs need to be adapted for each study/project.

14.2.39 Censoring reason

In order to summarize the various reasons for censoring, the following categories will be calculated for each time to event variable based on the treatment completion page, the study evaluation completion page and the survival page.

For survival the following censoring reasons are possible:

- Alive
- Lost to follow-up

For PFS and TTP (and therefore duration of responses) the following censoring reasons are possible:

- Ongoing without event
- Lost to follow-up
- Withdrew consent
- Adequate assessment no longer available*
- Event documented after two or more missing tumor assessments (optional, see [Table 14-7](#))
- Death due to reason other than underlying cancer
- Initiation of new anti-cancer therapy

*Adequate assessment is defined in [Section 14.2.25](#). This reason is applicable when adequate evaluations are missing for a specified period prior to data cut-off (or prior to any other censoring reason) corresponding to the unavailability of two or more planned tumor assessments prior to the cut-off date. The following clarifications concerning this reason should also be noted:

- This may be when there has been a definite decision to stop evaluation (e.g. reason="Sponsor decision" on study evaluation completion page), when patients are not followed for progression after treatment completion or when only UNK assessments are available just prior to data cut-off).
- The reason "Adequate assessment no longer available" also prevails in situations when another censoring reason (e.g. withdrawal of consent, loss to follow-up or alternative anti-cancer therapy) has occurred more than the specified period following the last adequate assessment.
- This reason will also be used to censor in case of no baseline assessment.

